13.3 Prior and Concomitant Medications

Prior and concomitant medications, categorized by ATC level 2 and preferred term (PT) according to WHO Drug (Version B3 Sep2020 or later), will be summarized separately. The number and percentage of subjects using each medication will be displayed together with the number and percentage of subjects using at least one medication within each medication group and subgroup. Each concomitant medication will be coded to a single ATC code, taking into account the indication for the use of the medication as documented on the CRF.

The summary of prior medications will include any medication with a stop date prior to vaccination (Day 1). Prior medications with a stop date more than 14 days prior to vaccination will not be included in the summary table, but will be listed. Concomitant medications are those with a start or end date on or after date of vaccination.

The concomitant medication summaries for each study part will be cumulative, so the summary for each part of the study will contain any concomitant medications taken during previous study parts.

13.4 Immunogenicity Analyses

13.4.1 Hypothesis Testing Strategy and Multiplicity

A formal hypothesis test is defined for the primary immunogenicity analysis, using a two-sided significance level of 5%. There will be adjustment for multiplicity for primary immunogenicity endpoints if statistical significance (p-value ≤ 0.05 for any of the comparisons between the 3 Lots) is reached. To adjust for multiplicity in statistical comparison between the 3 Lots, the PDIFF=ANOM and ADJUST=NELSON option in PROC GLM will be used which analyzes all differences with the average least squares mean difference among the Lots. ANOM tests whether the treatment means differ from the overall mean (also called the grand mean); and if the least squares means are correlated, the ADJUST=NELSON option in PROC GLM

uses the factor-analytic covariance approximation described in Hsu (1992) for the underlying quantile calculation.

13.4.2 Primary Immunogenicity Analysis

The primary immunogenicity analysis will be a comparison of the GMTs in the PP analysis set between the VLA1553 Lots 1, 2 and 3 at Day 29 (i.e. 28 days postvaccination) by ANOVA, using the factor Lot as a fixed effect and study center as a covariate. The ANOVA model will be applied to the log-transformed (natural log base e) μ PRNT values of the three Lots and the 95% CIs for the pair-wise ratios of the GMTs will be obtained by taking the anti-log of the resulting 95% CIs for the least square means differences. If these three pairwise 95% CIs for GMT ratios are all between [REDACTED] equivalence between the three commercial batches will be postulated.

The analysis will be performed on the PP analysis set and will be repeated on the Full analysis set.

For the PP analysis set there will be also produced the following graphical outputs:

- a line plot of the GMT at each study timepoint and treatment arm;
- a reverse cumulative distribution plot of the proportion of subjects by treatment arm.

13.4.3 Secondary Immunogenicity Analyses

The secondary immunogenicity analyses will be performed on the PP analysis set and repeated on the Full analysis set.

13.4.3.1 Comparisons of Geometric Means for Titer and Fold Increase

Secondary immunogenicity analyses will include the comparison of the GMTs between the three Lots at Day 1, Day 8, Day 85 and Month 6 post-vaccination by ANOVA using the factor Lot as a fixed effect and study center as a covariate, two-sided 95% confidence intervals will be calculated for the GMT. Day 1 values will be summarized to display values at baseline.

Values of geometric mean fold increase (GMFI) will be analyzed in the same way as for GMTs.

13.4.3.2 Seroprotection Rate

The number and percentage of subjects meeting the criteria for seroprotection will be presented for each study timepoint and treatment group. The denominator for the percentage will be the number of baseline negative μ PRNT subjects with non-missing NT values at each timepoint. Two-sided exact (Clopper-Pearson) 95% CIs for the seroprotection rate (SPR) will be presented.

The treatment groups will be compared using Fisher's Exact test. In addition, the pairwise difference in risk between the three treatment groups, and exact two-sided 95% CIs for the pairwise differences in risk between treatment groups will be presented.

This summary will be repeated by titer threshold, evaluating the number of baseline negative subjects meeting the criteria μ PRNT₅₀ \geq x, where x takes the values [REDACTED]

Bar charts of the percentage of subjects meeting the seroprotective criteria will be produced by study visit and treatment group.

13.4.3.3 Seroconversion Rate

The seroconversion rate (SCR) will be summarized similarly to the SPR, but will only be presented on Days 29 and 180.

13.4.3.4 Fold-Increase in Neutralizing Antibody Titer

The fold-increase will be summarized as a continuous endpoint in descriptive statistics. In addition, the number of subjects reaching pre-specified fold-increase categories of at least 4, 8, 16 and 64-fold increases compared to baseline will be summarized as the number and percentage of subjects in each category

13.4.4 [REDACTED]

13.4.4.1 [REDACTED]

13.4.4.2 [REDACTED]

13.4.4.3 [REDACTED]

13.4.4.4 [REDACTED]

13.5 Safety Analyses

Descriptive statistics will be used in all safety analyses, unless otherwise specified.

13.5.1 Adverse Events

Safety tabulations will generally be provided separately for solicited AEs and unsolicited AEs, and for both types of AEs combined. Number and proportion of subjects, plus number of events in each category will generally be presented. 95% confidence intervals will be provided for all AEs, SOC and PT. Differences between the three Lots will be assessed for significance using Fisher's exact test.

Summaries of AEs categorized by SOC and PT coded according to the MedDRA dictionary will be produced. Within these summaries counting will be by subject not event and subjects are only counted once within each SOC or PT.

Where AEs are presented by severity (Mild, Moderate, Severe), SOC and PT, subjects with multiple events within a particular body system or preferred term will be counted once under the category of their most severe event within that SOC or PT.

In summaries of AEs which are categorized by relationship to IMP, SOC and PT, AEs with a causality reported as probable or possible will be considered related to the IMP. Subjects with multiple events within a particular SOC or PT will be counted under the category of their most drug-related event within that SOC or PT.

All AE tabulations will be presented for the Safety analysis set.

All AEs recorded on the CRF will be listed.

Furthermore, the following tabulations of AEs will be produced:

- All unsolicited AEs up to study Day 29 will be presented by SOC and PT, as well as summaries by SOC, PT and severity. Treatment groups will be compared using Fisher's exact test (Part A);
- Solicited injection site and systemic AEs within 10 days post-vaccination by PT (Part A);
- Solicited injection site and systemic AEs within 10 days post-vaccination by PT and severity (Part A);
- All AEs during the entire study period by SOC and PT (Parts A, B);
- All AEs during the entire study period by SOC, PT and severity (Parts A, B);
- All Related AEs during the entire study period by SOC and PT (Parts A, B);
- SAEs by SOC and PT during entire reporting period (Parts A, B);
- Related SAEs by SOC and PT during entire reporting period (Parts A, B);
- AESI within 2 to 21 days post-vaccination by SOC and PT (Part A, B);
- AESI for ongoing events from Part A (Part B);
- Related AESI within 2 to 21 days post-vaccination by SOC and PT (Part A, B);

In addition, the following tables will also be presented for the specified study part:

- AE summary table showing the overall number and percentage of subjects with any AE, any related AE, any severe AE, any related severe AE, any solicited AE, any severe solicited AE, any related solicited AE, any related severe solicited AE, any solicited injection site AE, any severe solicited injection site AE, any solicited systemic AE, any severe solicited systemic AE, any unsolicited AE, any related unsolicited AE, any severe unsolicited AE, any related severe unsolicited AE, any SAEs, any related SAEs, any related solicited SAE, any related unsolicited SAE, any AESI as assessed by the investigator, any AESI as assessed by the DSMB, any related AESI as assessed by the investigator, any medically attended AE, any related medically attended AE, any related medically attended solicited AE, any related medically attended unsolicited AE, any AE leading to withdrawal from the study, any unsolicited AE leading to withdrawal from the study and any solicited AE leading to withdrawal from the study. For each study arm 95% CIs will be presented for percentages. Differences between the three Lots will be assessed for significance using Fisher's exact test (Parts A, B);
- AE summary table as above, split by whether the subject was ELISA seropositive or seronegative at baseline (Parts A, B);

- AE summary table as above, split by whether the subject was μ PRNT baseline seropositive (defined as [REDACTED] compared to baseline ELISA seropositive subjects)
- Unsolicited related AEs up to Day 29 by SOC and PT (Part A);
- Unsolicited related AEs up to Day 29 by SOC, PT and maximum severity (Part A);
- Solicited injection site and systemic AEs within 10 days post-vaccination by PT excluding recall data (Part A);
- Solicited related injection site and systemic AEs (Part A);
- Solicited related injection site and systemic AEs by maximum severity (Part A);
- AESI by SOC, PT and maximum severity (Part A, B);
- Related AESI by SOC, PT and maximum severity (Part A, B);
- Solicited local and systemic AEs tabulated by subject diary day up to Day 11. This tabulation will be based on onset day of the AE. If not possible to assign a day due to partial onset date then it will be assumed to be Day 1 (Part A);
- Summary of duration of solicited local and systemic AEs. Summary statistics for duration of solicited AE (days) will be presented by symptom in each study arm (Part A);
- Maximum fever temperature post-vaccination up to Day 11, for subjects who experienced fever (Part A);
- Unsolicited AEs by SOC and PT (Parts A, B);
- Unsolicited related AEs by SOC, PT (Parts A, B);
- Any unsolicited related severe AE by SOC and PT (Parts A, B);
- Any AE occurring at a frequency of at least 10% in at least one study arm by PT (Parts A, B);
- Any AE occurring at a frequency of at least 1% in at least one study arm by PT (Parts A, B);
- Any related AE occurring at a frequency of at least 10% in at least one study arm by PT (Parts A, B);
- Any related AE occurring at a frequency of at least 1% in at least one study arm by PT (Parts A, B);
- Any medically attended AE by SOC, PT (Parts A, B);
- Any medically attended AE by SOC, PT and Maximum Severity (Parts A, B);
- Any AE leading to withdrawal from study by SOC and PT (Parts A, B);

AE rates will be plotted in forest plots by treatment group for all AEs, severe (related) AEs, related AEs, SAEs and AESIs. Radar plots will be produced for subjects with solicited AEs, displaying the maximum severity of any AEs within each of the categories of solicited AE.

Subject diary data will be listed.

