15.5 Procedures for Monitoring Subject Compliance

All study procedures are to be performed under the supervision of the Investigator at the study site, and thus, no separate procedures will be used to monitor subject compliance.

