9.4 Analysis Sets

9.4.1 Safety Analysis Set

The safety analysis set (SAF) contains all subjects who entered into the study and received the vaccination. Subjects will be analyzed as treated.

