11.7.6 Solicited Adverse Events

Solicited AEs are defined only in the first 10 days post-vaccination (until study Day 11). All solicited AEs will be reported by the subject in the Subject eDiary and will be recorded on the AE page of the CRF. The same information on severity and causality will be collected for these events as for the unsolicited AEs and they will be coded in the same way. Only those solicited AEs recorded as such on the AE page of the CRF will be included in the main analysis of solicited AEs.

Any solicited adverse events which are reported on the AE page of the CRF but not reported on the eDiary are flagged as recall events. This flag is used in a sensitivity analysis of the solicited AEs.

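### The recall-excluded solicited AE table counts vaccinated subjects without eDiary data as reaction-free, so its rates are biased low by an amount the table cannot show

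*SAP*

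**What the plan says.** SAP 11.7.6 sets two rules for solicited events. The main analysis takes its events from the CRF: "Only those solicited AEs recorded as such on the AE page of the CRF will be included in the main analysis of solicited AEs". Solicited events "reported on the AE page of the CRF but not reported on the eDiary are flagged as recall events", and "This flag is used in a sensitivity analysis of the solicited AEs".

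SAP 13.5.1 then lists the sensitivity table, "Solicited injection site and systemic AEs within 10 days post-vaccination by PT excluding recall data (Part A". That bullet gives no denominator. The general sentence in the same section supplies one: "All AE tabulations will be presented for the Safety analysis set". SAP 9.4.1 defines that set without any diary condition: "The safety analysis set (SAF) contains all subjects who entered into the study and received the vaccination".

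Two other places bear on the point. SAP 11.8 bases analyses on observed values and generally does not impute missing ones; it has no rule for absent or incomplete eDiaries. SAP 13.4.3.2 restricts the seroprotection denominator to subjects with a non-missing titer at the time point. The solicited table has no comparable restriction.

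**The concern.** Once recall events are removed, a reaction can be seen only through the eDiary. A vaccinated subject without eDiary data who tells the investigator about a fever has, by definition, a recall event. The event is dropped and the subject remains in the denominator. In effect the table imputes no reaction for that subject, which sits badly with the rule in SAP 11.8.

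What is at stake is how the sensitivity table can be read. The gap between the main rate and the recall-excluded rate mixes two things: events that diary users reported later, and subjects who had no diary at all. The first concerns recall; the second is missing data. With no count of subjects who have eDiary data, a reader cannot separate them.

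**Working it through.** The plan states no recall-excluded rate, diary completion rate or bias, so there is no figure of its own to reproduce.

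**Inputs**
- Denominator: all vaccinated subjects (SAP 9.4.1 and 13.5.1).
- Numerator: subjects with a solicited event that is in the eDiary (SAP 11.7.6).
- Illustrative reaction rates: Phase 1 medium-dose group, Protocol 10.5.3: any solicited systemic reaction 40.0%, headache 23.3%, fever 20.0%, injection site 6.7%.
- m, the share of vaccinated subjects with no eDiary data: not in the documents. Assumed range 5% to 20%.

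**Formulas**

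Let p_d be the reaction rate in subjects with a diary and p_m the rate in those without. Suppose first that diary users record all their reactions.
- Reported rate = (1 − m) × p_d
- True rate = (1 − m) × p_d + m × p_m
- Absolute shortfall = m × p_m
- Relative shortfall = m × p_m / true rate, which equals m only when p_m = p_d

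**Missingness unrelated to reactions (p_m = p_d = p; reported rate = p × (1 − m))**

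| Reaction | True rate | m = 5% | m = 10% | m = 20% |
|---|---|---|---|---|
| Fever | 20.0% | 19.0% | 18.0% | 16.0% |
| Headache | 23.3% | 22.1% | 21.0% | 18.6% |
| Any systemic | 40.0% | 38.0% | 36.0% | 32.0% |
| Injection site | 6.7% | 6.4% | 6.0% | 5.4% |

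**Missingness related to reactions (p_d = 40%, m = 10%)**

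The reported Safety-set rate is 0.90 × 40% = 36.0% in every row. The rate on a diary-based denominator is 40.0% in every row.

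| p_m | True rate | Safety-set shortfall (relative) | Error of diary-based rate |
|---|---|---|---|
| 0% | 36.0% | 0 points (0%) | +4.0 points |
| 20% | 38.0% | 2.0 points (5.3%) | +2.0 points |
| 40% | 40.0% | 4.0 points (10%) | 0 |
| 60% | 42.0% | 6.0 points (14.3%) | −2.0 points |

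Neither denominator is right in all cases. The Safety-set rate is exact only if subjects without a diary never react. The diary-based rate is exact only if they react like everyone else.

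**How the gap mixes two sources**

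Take p = 40% in all subjects and m = 5%, let 10% of reactors with a diary fail to record the event there, and suppose the CRF captures every reaction.
- Main rate: 40.0%.
- Recall-excluded rate on the Safety set: 0.40 × 0.95 × 0.90 = 34.2%.
- Gap: 5.8 points, of which 0.05 × 40% = 2.0 points come from absent diaries and 0.95 × 40% × 0.10 = 3.8 points from late reports by diary users.
- Recall-excluded rate on the diary-based denominator: 0.40 × 0.90 = 36.0%.

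The planned table would show only 40.0% and 34.2%. Adding the diary-based rate and the count behind it lets the reader see how much could come from absent diaries.

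**The case against.** The strongest defence is that one fixed denominator is a legitimate choice. With it, the main rate minus the recall-excluded rate is exactly the share of subjects counted only through recall, and because removing events can only lower a rate, the table reads naturally as a lower bound. The SAP does not say what the sensitivity analysis is meant to show. Restricting to diary users conditions on behaviour after vaccination and can introduce its own bias, as the second table shows. All of this stands. It is a reason to keep the Safety-set rate, but it does not tell a reader how much of the difference comes from absent diaries.

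Four stronger readings are tempting, and the documents do not support them.
- A reader might infer that the by-diary-day table has the same fault. SAP 13.5.1 builds that table on AE onset day and does not exclude recall events, so a subject without an entry can still be counted. Limiting its denominator to subjects with an entry that day would create a mismatch between numerator and denominator.
- A reader might infer that uneven diary completion would produce spurious lot differences in Fisher's test. Chance imbalance between randomized lots is part of the sampling variation the test already covers. Only systematic differences by lot would bias it, and Protocol 12.4 and 12.4.1 keep subjects and site staff blinded.
- A reader might take Protocol 15.5, where "no separate procedures will be used to monitor subject compliance", to mean that nothing limits missing diaries. That sentence concerns procedures supervised at the site. Protocol 17.3 has the investigator review the questionnaires with the subject and see that self-reporting is complete. This should reduce m, but it sets no analysis rule, and an event recovered verbally at that review and not in the eDiary would itself be flagged as recall.
- A reader might infer that the relative bias always equals the missing share. That holds only when p_m = p_d.

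**Conclusion.** The point holds for one Part A sensitivity table. Read together, SAP 9.4.1, 11.7.6 and 13.5.1 make vaccinated subjects without eDiary data count as reaction-free there, so by this route the rate can only be too low. The denominator follows from the general sentence in SAP 13.5.1, not from the bullet itself.

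The size is m × p_m in absolute terms and cannot be fixed from the documents, because m is not given. For a 40.0% systemic rate and m between 5% and 20%, with missingness unrelated to reactions, it is 2.0 to 8.0 points; for a 6.7% injection-site rate it is 0.3 to 1.3 points. If missingness is related to reactions, it may be smaller or larger.

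The main solicited analysis keeps recall events and is not affected by this route, nor is the primary endpoint. The effect falls on the absolute rates in this table and on what its gap from the main analysis can be taken to mean.

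**What to change.** In SAP 13.5.1, for the recall-excluded solicited table only:
- keep the Safety-set rates and add, beside them, rates with the denominator limited to subjects with at least one eDiary entry in the solicited window;
- report per lot the number of subjects with no eDiary data and the number with incomplete eDiary data.

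No change is needed to the by-diary-day table or the main solicited tables.

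The cost is a sentence or two of SAP wording and a flag derived from eDiary data already held, since SAP 13.5.1 already lists the diary data. The added rates have slightly wider confidence intervals because fewer subjects contribute. They are themselves biased if diary completion is related to reactions, and the one-entry criterion does not deal with partly completed diaries. Hence both denominators are shown and incomplete diaries are counted.

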The eQuestionnaires will serve as source documentation. Entries in the eQuestionnaires will be transcribed into the appropriate eCRFs. Any entry on the eCRF that does not correspond with an entry in the eDiary will be explained by the Investigator on the relevant questionnaire page.

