11.7 Adverse Events

An AE is defined as any untoward medical occurrence in a subject administered an investigational product that does not necessarily have a causal relationship with the treatment. All new abnormalities or any exacerbation in intensity or frequency (worsening) of a pre-existing condition during or after vaccination have to be documented as AEs.

Any untoward medical occurrence experienced before vaccine exposure (for example, from the time of signed informed consent up to but not including vaccine exposure) will not be considered an AE and will be described in the medical history.

A subject's death per se is not an event, but an outcome. The event which resulted in the subject's death must be fully documented and reported, regardless of being considered related to treatment or not.

Preexisting diseases that are described in the medical history, and that manifest with the same severity, frequency, or duration after vaccine exposure, will not be recorded as AEs. However, when there is an increase in the severity of a preexisting disease, the event will be recorded as an AE.

There is no definition of treatment-emergent in this study. Any AEs with an onset date prior to the date of vaccination will be raised with data management and should be moved to medical history.

All AEs entered on the CRF will be coded according to the Medical Dictionary for Regulatory Activities (MedDRA) Version 23.1 or higher. The following information will be documented on the CRF for each AE: severity, causality, outcome, seriousness, medically-attended, action taken to treat AE, start and stop dates.

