11.9 Handling of Missing or Incomplete Dates

Missing or partial dates will not be imputed, except to determine the timing of AEs or concomitant medications in relation to VLA1553 dosing.

Untoward medical occurrences with missing or partial start dates will be considered AEs unless the partial start date indicates that the event began prior to vaccination with VLA1553, e.g. if the month and/or year are before the month of Visit 1.

Medications with incomplete end dates will only be considered prior if the partial end date indicates that the medication was stopped prior to dosing, e.g. if the month and/or year are before the month of Visit 1. All other medications with missing or incomplete end dates will be considered concomitant.

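### The solicited-AE onset table puts every event with an undeterminable onset day on Day 1, so any such events can only inflate Day 1 and deplete Days 2 to 11

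*SAP*

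**What the plan says.** SAP 13.5.1 lists this output for Part A: "Solicited local and systemic AEs tabulated by subject diary day up to Day 11. This tabulation will be based on onset day of the AE". The next sentence gives the rule for incomplete dates: "If not possible to assign a day due to partial onset date then it will be assumed to be Day 1".

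Four other provisions bear on it.

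- **Source of the events.** SAP 11.7.6 builds the solicited analysis from the CRF, not the diary: "Only those solicited AEs recorded as such on the AE page of the CRF will be included in the main analysis of solicited AEs". Events "reported on the AE page of the CRF but not reported on the eDiary are flagged as recall events", so they are part of the main solicited analysis.
- **Dates on the CRF.** SAP 11.7 lists what is documented for each AE, ending with "action taken to treat AE, start and stop dates". Every solicited event, recall or not, therefore has a CRF start-date field.
- **Partial dates in general.** SAP 11.9 says: "Missing or partial dates will not be imputed, except to determine the timing of AEs" or concomitant medications in relation to dosing.
- **Sensitivity output.** SAP 13.5.1 plans a version excluding recall data for the table by preferred term. It lists none for the table by day.

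**The concern.** A table of onset by day has one job, which is to show when reactions begin. A solicited event with no assignable onset day could have started on any day of the solicited period. Placing all such events on the first day asserts something the data do not show, and it does so in the reported quantity itself.

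Day 1 is not a cautious default here. It adds no subject and no event to any count; it only changes when the event appears to have begun. For a replicating vaccine the time course of fever, myalgia and arthralgia has descriptive interest: Protocol 10.2.1 puts symptoms of natural CHIKV disease at usually 4 to 7 days after infection.

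The planned output would not reveal the effect. It has no row for unknown onset, no stated count of assumed days and no recall-excluded version. A reader could not separate observed Day 1 onsets from assumed ones within the table.

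As worded, the rule also makes no exception where the known part of the date rules Day 1 out, for example when the recorded month is the one after vaccination.

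**Working it through.** The plan states no figure to reproduce: no number of partial onset dates, no number of recall events and no expected onset distribution. Only direction and scale can be checked.

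**Direction.** Let f be the share of solicited events whose onset day cannot be assigned and p1 the true share starting on Day 1. Assume that having an unassignable day is unrelated to the true onset day.

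- Day 1 share shown = p1(1 − f) + f
- Excess over the truth = p1(1 − f) + f − p1 = f(1 − p1)

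This is never negative, and Days 2 to 11 together lose the same amount. If the undated events have a different onset pattern, p1 in the excess is replaced by the Day 1 share among the undated events. The excess is still never negative, and it vanishes only if f = 0 or all undated events truly began on Day 1.

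**Scale (illustration).** Inputs from the documents:

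- 134 subjects per lot (SAP 8.0)
- 40.0% with a solicited systemic reaction in the Phase 1 medium-dose group (Protocol 10.5.3)

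Counting one event per reacting subject, which is an assumption, gives 134 × 0.40 = 53.6 events per lot. The values of f and p1 are also assumed. The lowest p1, 1/11, corresponds to onset spread evenly over the 11 tabulated days.

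Excess Day 1 events per lot = 53.6 × f × (1 − p1):

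| f | p1 = 1/11 | p1 = 20% | p1 = 40% |
|---|---|---|---|
| 0 | 0 | 0 | 0 |
| 1% | 0.49 | 0.43 | 0.32 |
| 2% | 0.97 | 0.86 | 0.64 |
| 5% | 2.44 | 2.14 | 1.61 |
| 10% | 4.87 | 4.29 | 3.22 |

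For p1 = 20% the true Day 1 count is 53.6 × 0.20 = 10.7. The table would show 11.2, 11.6, 12.9 and 15.0 events at f = 1%, 2%, 5% and 10%, which are Day 1 shares of 20.8%, 21.6%, 24.0% and 28.0%.

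**Reach.** The Day 1 assumption appears in one bullet, for one table. Setting it beside the other outputs:

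- Tables by preferred term and by severity count subjects with events in the solicited period and do not use the onset day within it.
- AESIs are identified by the investigator, analysed only if flagged as such on the CRF, and adjudicated by the DSMB (SAP 11.7.5).
- Duration is end date minus onset date plus one, with a substitution rule only for a missing end date (SAP 11.7.7). The duration bullet in 13.5.1 does not refer to the Day 1 assumption.
- The primary GMT analysis uses no AE data.

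**The case against.** The strongest objection is that the rule may never be used. The eDiary is completed daily, the CRF has a start-date field for every AE, and Protocol 17.3 has the investigator review the questionnaires with the subject at the next visit. It adds: "Any entry on the eCRF that does not correspond with an entry in the eDiary will be explained by the Investigator". The rule is disclosed, applies identically to all three lots, and sits beside full listings of AEs and of diary data, so anyone with the listings can check it. Its conditional wording also leaves room to assign a day from other information first.

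Most of this stands, and it is why the point is minor. It does not make Day 1 a good default when the rule is used, and the wording does not tell the programmer to consult the eDiary first.

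Four stronger readings may tempt a reader. The documents support none of them.

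- **That recall events are the main cause because they have no date.** Lacking an eDiary entry is not lacking a CRF start date. A recall event meets the rule only if its CRF date is itself partial. Some may be reactions seen during the post-vaccination observation at the site (Protocol 15.3.3), with the day known. Recall events are a plausible source of partial dates, no more.
- **That Day 1 assignment takes events out of the 2-to-21-day AESI period.** AESI status comes from the investigator's flag and DSMB adjudication, not from this table.
- **That the assumed Day 1 lengthens reported durations.** Nothing in the SAP carries it into the duration summary.
- **That the rule contradicts SAP 11.9.** The exception there for AE timing relative to dosing can be read to cover it.

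**Conclusion.** The point holds as a small, conditional one. Whenever the rule is used for an event that did not truly begin on Day 1, the onset-by-day table overstates Day 1 and understates later days, and nothing in the table shows by how much.

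The size cannot be derived from the documents. In the illustration it runs from 0.3 to 4.9 events per lot. That range rests on assumed partial-date rates of 1% to 10%, assumed Day 1 shares of 1/11 to 40%, one event per reacting subject, and date completeness unrelated to onset day. With no partial dates it is zero.

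The effect is confined to one descriptive Part A safety table. No endpoint, event rate, lot comparison of GMTs or safety conclusion depends on it. It is worth changing because the change is cheap, not because the expected distortion is large.

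**What to change.** In SAP 13.5.1, replace the Day 1 assumption with a two-step rule. Where the onset date is partial, use the first eDiary day on which the symptom is recorded, if there is one. Otherwise count the event in a row labelled 'onset day unknown'.

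The first step helps events that are in the eDiary but have an incomplete CRF date. It cannot help recall events, which by definition have no eDiary entry; any of these with a partial date would go to the unknown row, where their number is visible.

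The cost is one SAP sentence and one table row. A few events may no longer be assigned to a specific day, which reflects what is known about them.
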